7. STATISTICAL METHODS AND ANALYSIS OF THE INITIAL TREATMENT

Analyses for the initial treatment period (defined in Section 6) will be performed based on the modified ITT population as defined in Section 5.1, unless otherwise specified. Outputs will display summaries for subjects with DLL3 high and DLL3 positive (per Ventana rabbit SP347 IHC assay specification), respectively.

7.1 *Subject Disposition*

The number and percent of subjects in each analysis population group will be summarized. The number and percentage of treated subjects, subjects discontinuing from study treatment during initial treatment, including the reasons for study drug discontinuation during initial treatment, subjects discontinuing the study, including the

reasons for discontinuation from the study, and subjects in the follow-up or retreatment period will be presented. Detailed information will be listed.

7.2 Study Conduct

Protocol violations and major protocol deviations will be summarized.

7.3 Demographics, Baseline Characteristics and Prior Therapies

Demographic characteristics including age, sex, race and ethnicity; as well as baseline characteristics including height, weight, ECOG performance status, history of brain metastases, presence of brain metastases at baseline, and smoking history will be summarized and listed. Summaries of subgroups included in Section 5.3 will also be provided.

Disease history data, including stage at initial diagnosis and at study entry, history of paraneoplastic syndrome, number of metastatic sites, location of metastatic sites, and time from diagnosis to first dose will be summarized and listed.

Medical history being coded with MedDRA will be summarized by system organ class and preferred term. Medical history will be listed as well.

Prior systemic therapy, prior radiation, and prior surgery defined in Section 4.1 will be summarized and listed.

7.4 Treatment Exposure and Compliance

Exposure to study treatment will be summarized and listed:

- Cumulative actual dose (mg)
- Treatment duration (cycles)

The number and percent of subjects with at least one dose modification (reduced, interrupted or delayed) will be summarized, which will include dose modification due to AE and other reasons. Dose modifications and study treatment discontinuation due to adverse events captured on AE CRF will be summarized in separate adverse event tables.

7.5 *Analysis of Primary Efficacy Endpoint*

All analyses of primary efficacy endpoints will be summarized for the modified ITT and efficacy evaluable populations defined in Section 5.

7.5.1 Objective Response Rate

Overall Response at each visit post-baseline is assessed based on a subject's lesion measurements or assessments. Overall Response is assessed as CR, PR, SD, PD, or NE as defined by RECIST version 1.1. An additional category of Early Death will also be included which is defined as subjects who died prior to any post-baseline response assessment. Amongst all the Overall Responses, the best Overall Response is then determined. The best Overall Response will be ordered as CR, PR, SD, PD, or NE; with CR being the best. A subject will be considered to have a best overall response of SD if there is a minimum interval of 42 days between the date of assessment and (-7 days to allow for scheduled visit window per the protocol) the first dose date. Subjects who died prior to the first post-baseline lesion assessment are included in the Early Death category. The Not Evaluable (NE) category includes subjects who are not evaluable as indicated by the IRC or by the Investigator, in analyses of overall response per IRC and investigator, respectively. Subjects who discontinued the study prior to obtaining a post-baseline scan for lesion assessment will be categorized as Indeterminate.

Objective Response is defined as a subject with the best Overall Response of Complete Response (CR) or Partial Response (PR) prior to receiving any subsequent anticancer therapy and retreatment, and is confirmed by a consecutive response assessment at least 4 (28 days) from the initial determination of CR/PR per RECIST v 1.1 as described in Table 1:

Table 1 – Confirmed partial and complete response

Overall response First time point	Overall response Subsequent time point	BEST overall response
CR	CR	CR
CR	PR	SD, PD or PR ^a
CR	SD	SD (if minimum duration for SD met), otherwise, PD
CR	PD	SD (if minimum duration for SD met), otherwise, PD

CR	NE	SD (if minimum duration for SD met), otherwise, NE
PR	CR	PR
PR	PR	PR
PR	SD	SD
PR	PD	SD (if minimum duration for SD met), otherwise, PD
PR	NE	SD (if minimum duration for SD met), otherwise, NE
NE	NE	NE

Note: In case of SD, measurements must have met the SD criteria at least once after study entry at a minimum interval of 42 days (-7 days to allow for scheduled visit window per the protocol).

a If a CR is truly met at first time point, then any disease seen at a subsequent time point, even disease meeting PR criteria relative to baseline, makes the disease PD at that point (since disease must have reappeared after CR). Best response would depend on whether minimum duration for SD was met.

Only assessments within the initial treatment period will be included if a subject had retreatment. ORR is defined as the proportion of subjects with Objective Response. Best Overall Response Rate is defined as the proportion of subjects with a response of CR or PR (regardless of confirmation) prior to receive any subsequent anticancer therapy or retreatment.

ORR will be presented as a number and percentage with two-sided exact 95% binomial confidence interval (CI). Any subjects not exhibiting a response (CR or PR) as defined above are considered non-responders.

Similar analyses as described above will include:

- Best Overall response of CR or PR determined by the IRC
- ORR determined by the Investigator
- Best Overall response of CR or PR determined by the Investigator

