This study has two co-primary endpoints:

- Objective response rate through the End of Treatment (42 ± 3 days after last dose) for DLL3 high and for DLL3 positive, per IHC assay specification subjects
- Overall survival for DLL3 high and for DLL3 positive, per IHC assay specification subjects

Secondary:

- Duration of response for DLL3 high and for DLL3 positive subjects, per IHC assay specification
- Clinical Benefit Rate for DLL3 high and for DLL3 positive subjects, per IHC assay specification
- Progression-free survival for DLL3 high and for DLL3 positive subjects, per IHC assay specification

Safety Endpoints

Safety assessments include vital signs, body weight, ECOG score, clinical adverse events, laboratory tests (hematology, serum chemistries, urinalysis, and coagulation), ECGs, echocardiogram, fluid retention questionnaire, and monitoring of concomitant therapies.

Pharmacokinetic and Pharmacodynamic Endpoints

Pharmacokinetic assessments will include blood samples for rovalpituzumab tesirine and anti-therapeutic antibodies (ATAs).

Pharmacodynamic and biomarker assessments will include analyses of tumor tissue for DLL3 expression, and of blood samples for tumor markers, [REDACTED] and soluble biomarkers such as soluble DLL3.

STATISTICAL METHODS:

Sample Size

A response rate of 15% or less is typically observed in this advanced state of the disease. It is assumed that at least 25% of subjects treated with rovalpituzumab tesirine will achieve complete or partial response. In Stage 1, up to 60 evaluable, DLL3 high (per IHC assay specification), subjects may be enrolled. In Stage 2, at least 63 additional subjects that are DLL3 high (per IHC assay specification) will be enrolled, to maintain an 80% power at a one-side significance level of 0.025. The number of subjects evaluated at each stage and the minimum

number of responders to continue from Stage 1 to Stage 2 were estimated using the minimax principle of the Simon two-stage design.

Up to approximately 123 DLL3 high, third-line subjects will be enrolled. The total sample size for this study will be determined by the proportion of enrolled subjects with DLL3 high expression among those who are DLL3 positive.

Efficacy Analysis

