5.2.3 Dose Modifications

5.2.3.1 Treatment Delays Due to Toxicity or Progression

Subjects who experience toxicity during a cycle must have recovered as outlined previously in Section 5.2.2 before the next cycle may proceed. If an AE is still ongoing at the time of the next scheduled cycle, the cycle must be delayed until recovery. Specific recommendations are given below.

In the event of isolated CNS progression during study treatment, rovalpituzumab tesirine may be withheld while palliative treatment is administered, e.g., a standard course of whole brain radiotherapy in accordance with institutional practice. During this time, the subject should be fully evaluated for other sites of PD. If progression is isolated to the CNS, study drug may be restarted 1 week after the completion of radiotherapy. If more than 6 weeks have elapsed since the previous dose of study drug, the subject should undergo a radiographic tumor assessment. If additional sites of PD are present, the subject will be required to discontinue study drug, but may be eligible for retreatment.

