7.2 Response/Efficacy Assessments

Treatment response will be assessed by radiographic tumor evaluation at protocol-specified time points. Diagnostic quality, spiral CT scans are recommended; other methods may be used if performed consistently throughout the study for each individual subject. Scans of the chest, abdomen and pelvis must be obtained; scans of the neck must also be obtained if there is documented or suspected involvement in this region. Positron emission tomography (PET) may be used in an ancillary manner; however, no decisions relating to PD may be made based on PET alone. Clinical response will be determined by the investigator at each assessment according to

RECIST v1.1 (Appendix 12.4 and Eisenhauer 2009) and by Central Radiographic Assessment (Section 7.2.1).

Treatment at Cycle 2 beyond what would be considered progression of disease using RECIST v1.1 is permitted if the following criteria, as assessed by the investigator, are met:

[figure not shown]
- Ongoing clinical benefit, without rapid disease progression
- Subject continues to meet all other study protocol eligibility criteria
- Tolerance of study drug
- Stable ECOG performance status

Treatment beyond progression must not delay an imminent intervention to prevent serious complications of disease progression (e.g., central nervous system metastases).

Subjects' clinical data must be available for CRF source verification. Copies of tumor images must be made available for review by the sponsor or its designee upon request.

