6. ANALYTIC DEFINITIONS

Initial Treatment Period includes all assessments prior to the retreatment period or the start of new anti-cancer therapy, whichever occurs earlier. For subjects who will not be retreated, the initial treatment period will include assessments till the start of new anti-cancer therapy or the end of study, whichever occurs earlier.

Baseline Evaluation is the last available evaluation prior to receiving first dose of study drug. This will include any unscheduled evaluation prior to first dose. For subjects receiving retreatment, baseline for that period is the last available evaluation prior to receiving first dose of study drug for retreatment.

Change from Baseline is defined as the difference between the baseline value as defined above and the value at the respective time point. Negative values represent decreases from baseline; positive values will reflect increases from baseline.

Percent Change from Baseline is defined as the change from baseline divided by the baseline value times 100%. That is

$$100x (\text{Post-baseline value} - \text{baseline value}) / (\text{baseline value}).$$

Age at Baseline (in years) is defined from date of birth to date of first dose.

Last Evaluable Disease Assessment, for purpose of censoring, will be the last assessment with a response that is determined to be CR, PR, SD, PD, or Not Evaluable (NE).

Treatment-Emergent Adverse Event during this period is defined as any adverse event occurring on or after initiation of therapy and prior to the earlier of the start of retreatment period for those received Rova-T retreatment and the start of a subsequent anti-cancer therapy. Any adverse event with onset on or after the first dose of retreatment till the start of the next retreatment period or the start of a subsequent anti-cancer therapy will be considered treatment-emergent for that retreatment period.

Concomitant Medication is defined as a medication or treatment other than the study drug is considered concomitant if it is taken at any time on or after the first dose date. A medication taken prior to first dose date and continuing past first dose date is considered concomitant. Concomitant medications that stopped prior to first dose of retreatment will only be included in the initial treatment period. Medications started after the first of retreatment will be considered concomitant during the retreatment period.

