7.6.1 Duration of Response

Duration of objective response is defined as the time in months from the initial CR or PR to the time of disease progression or death on study, whichever occurs first during the initial treatment period. Only subjects with a confirmed response of CR or PR will be included.

For subjects who are alive and have not experienced disease progression on the study, duration of objective response will be censored at the day of the last tumor assessment during the initial treatment period. If no tumor assessment after the initial response is available, then the duration of response will be one day. Censoring rules for duration of response will be performed as detailed in [Table 3](#). If multiple visits exist, the latest

evaluable assessment date will be used for censoring except for PD, which will use the earliest assessment date when PD was recorded. Symptomatic deterioration will not be considered PD since a lesion assessment will need to be performed to verify disease progression. If there are multiple scans with multiple dates provided for a visit, the lesion assessment date will be the last scan date recorded for that visit to define baseline and the earliest scan date within the visit to determine the lesion assessment date post-baseline.

Table 3 - Duration of Response Censoring Methodology

Situation	Date of Progression/Death or Censoring	Outcome*
Death or disease progression per RECIST 1.1 at any time during initial treatment period	Date of death or first disease assessment showing disease progression, whichever occurs first	Event
Progression caused by new lesion during initial treatment period	Date new lesion is detected	Event
Progression caused by worsening of non-target lesion(s) or target lesion(s) during initial treatment period	First assessment date documenting the increase in target lesion(s) meeting criteria for progression, or the worsening non-target lesion(s)	Event
Progression caused by multiple causes (e.g. new lesions and worsening of non-target lesions) during initial treatment period	First date among the multiple sources of PD	Event
Subsequent anti-cancer treatment started before death or without documentation of disease progression beforehand	Date of last evaluable disease assessment prior to start of subsequent anti-cancer treatment	Censored

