7.6.2 Clinical Benefit Rate

Clinical Benefit is defined as the achievement within a subject of a Best Overall Response of CR, PR or SD with SD of a minimum duration of 42 days (-7 days to allow for scheduled visit window per the protocol) from the first dose date, prior to receiving any subsequent anticancer therapy and retreatment; as defined by RECIST version 1.1. CBR is defined as the proportion of subjects with clinical benefit. CBR will be presented as a number and percentage with two-sided exact 95% binomial confidence interval (CI). CBR will be summarized based on IRC assessments, and based on investigator assessments, respectively.

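### First progression does not close the SAP's response window, so a PR or SD recorded after permitted dosing beyond progression counts towards the response and clinical benefit rates

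*SAP*

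**What the plan says.** **Dosing after progression.** Protocol 7.2: "Treatment at Cycle 2 beyond what would be considered progression of disease using RECIST v1.1 is permitted", on investigator-assessed criteria. Protocol 5.2.3.1 adds a second route: "If progression is isolated to the CNS, study drug may be restarted 1 week after the completion of radiotherapy".

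**Imaging after progression.** Protocol 6.4 includes CT at the EOT visit. It may be omitted if a disease assessment was done in the last 6 weeks, but there is no exception for subjects who have progressed. Note 21 to the schedule of assessments, in both documents, has disease assessments run until progression or new therapy, after which only later therapies, progression date and survival status are collected. Protocol 6.5 limits follow-up imaging to subjects without centrally confirmed progression. SAP 9 includes scans from unscheduled visits.

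**Response.** SAP 7.5.1 chooses the best response from all post-baseline overall responses, in the order CR, PR, SD, PD, NE. An objective response must occur "prior to receiving any subsequent anticancer therapy and retreatment, and is confirmed by a consecutive response assessment" at least 28 days later. A second rate counts CR or PR without confirmation. SAP 6 sets the window: "Initial Treatment Period includes all assessments prior to the retreatment period or the start of new anti-cancer therapy, whichever occurs earlier", running to new therapy or end of study for subjects not retreated. SAP 7.6.2 uses the same two cut-offs for clinical benefit ("prior to receiving any subsequent anticancer therapy and retreatment; as" defined by RECIST) and requires SD at least 42 days (less a 7-day allowance) after first dose. Protocol 9.2.6.1.1 takes the highest response recorded through EOT.

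**Duration.** SAP 7.6.1, Table 3, dates the event at "Date of death or first disease assessment showing disease progression, whichever occurs first". SAP 7.6.3 applies Table 3 to duration of clinical benefit (DOCB).

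**The concern.** The plan expects some subjects to be dosed after progression, so it has to say what a later scan does to their best response. As written, a later PR or SD outranks the earlier PD. Table 1 of SAP 7.5.1 has no row that starts with PD, and its footnote deals only with disease reappearing after a CR. Neither Protocol Appendix 12.4 nor Protocol 9.2.6.1.1 supplies a stop at PD.

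Two things are at stake. First, the omission can move response and benefit rates in one direction only, in a single-arm trial set against a fixed rate: "A response rate of 15% or less is typically observed in this advanced state of the disease". Second, the endpoints stop agreeing with one another: one subject can be a PFS event at the Cycle 1 scan and a responder, or a clinical benefit subject, at EOT.

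**Working it through.** **1. One subject followed through the rules.** Assume PD at the scan before Cycle 2 on Day 40 (schedule note 3: Days 36–42), a second dose under Protocol 7.2, and PR at EOT on Day 84. The scans are 84 − 40 = 44 days apart, so the 6-week omission rule does not remove the EOT CT.

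| Analysis | Result as written |
|---|---|
| PFS (SAP 7.6.4) | Event at Day 40 |
| Protocol ORR (9.2.6.1.1) | Responder; the EOT scan is enough |
| Unconfirmed CR/PR rate (SAP 7.5.1) | Responder; the EOT scan is enough |
| CBR (SAP 7.6.2) | Clinical benefit; SD at EOT would also be enough, since Day 84 is past the 42-day minimum |
| Confirmed ORR, investigator | Responder if confirmed at least 28 days later; scheduled scans continue if the central reader did not call PD |
| Confirmed ORR, central review | Responder only if an unscheduled scan confirms, because scheduled imaging stops after centrally confirmed PD |

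**2. Effect per subject.** 1/123 = 0.8 percentage points in the full DLL3 high group; 1/60 = 1.7 points at Stage 1, where 9 responders stop enrolment and 10 continue it.

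**3. Duration, reading Table 3 literally.** Time = (date of PD − date of first response + 1)/30.44.
- Day 40 and Day 84: (40 − 84 + 1)/30.44 = −43/30.44 = −1.4 months.
- Range over the visit windows (PD scan Day 36–42, Cycle 2 dose Day 41–45, EOT 39–45 days later, so Day 80–90): from (42 − 80 + 1)/30.44 = −1.22 to (36 − 90 + 1)/30.44 = −1.74 months. At the first of these ends the scans are 38 days apart and the EOT CT could be omitted.

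An unconfirmed PR enters DOCB and the duration of best overall response. It enters duration of objective response (DOR) only if confirmed.

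**4. The stated design, reproduced.** Inputs from the Protocol synopsis: null rate 15%; "It is assumed that at least 25% of subjects treated with rovalpituzumab tesirine will achieve complete or partial response"; one-sided 0.025; 80% power; minimax Simon design; 60 subjects, continue if more than 9 respond, 123 in total. An exact search finds no design for n = 110 to 122. At n = 123 it returns 60 subjects, more than 9 to continue, and more than 26 of 123 at the end, with alpha 0.0242 and power 0.8001. The final cut-off of 27 or more comes from this search; the readable text gives none.

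**5. Illustration only.** Let X1 be the Stage 1 responders and p the 15% rate plus an assumed share of post-progression responders. P(positive) = P(X1 > 9 of 60 and total ≥ 27 of 123).

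| Added share | p | P(pass Stage 1) | P(positive) |
|---|---|---|---|
| 0 | 0.15 | 0.412 | 0.024 |
| 1 point | 0.16 | 0.498 | 0.049 |
| 2 points | 0.17 | 0.581 | 0.090 |
| 3 points | 0.18 | 0.658 | 0.148 |

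Three points of 123 is 0.03 × 123 = 3.7, or about four subjects.

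**The case against.** The case for the plan is mainly about reach, and most of it stands.

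- **Imaging may stop at PD.** Note 21 points that way and Section 6.4 does not. The documents conflict, so an EOT scan after PD cannot be taken as certain. Neither can it be excluded.
- **Confirmed central ORR is largely protected.** It needs a PR at EOT plus an unscheduled confirming scan. A reader might infer from the table in step 5 that error on this endpoint rises from 2.4% to as much as 14.8%. The documents do not support that: the added shares are assumed, the cut-off is derived, and the planned ORR analysis is an estimate with an exact 95% interval.
- **Such responses are limited by RECIST.** Appendix 12.4 makes any new lesion PD, so a subject who progressed by a new lesion does not become PR or SD while it persists. This lowers the frequency but does not remove the gap.
- **The CNS route is uncertain.** New anti-cancer therapy is not defined, and Protocol 4.1 lists radiation among the prior therapies needing a washout. Brain radiotherapy may already close the window.
- **A negative duration is not inevitable.** DOR runs from response to progression, which can be read as the first PD after response, and the earliest-date sentence in SAP 7.6.1 may be a convention for choosing among scan dates. That reading avoids the negative value but leaves the subject progressed for PFS before becoming a responder. The one-day rule in SAP 7.6.1 does not settle it: it sits in the paragraph on subjects who have not progressed and covers responders with no later scan.

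An appeal to RECIST v1.1 in general does not close the gap. SAP 7.5.1 applies it through Table 1, which omits this sequence, and the SAP writes out its other two cut-offs.

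**Conclusion.** The gap is real on the text and should be closed. A PR or SD recorded after first PD counts towards the unconfirmed CR/PR rate, CBR, DOCB and the protocol's EOT-based ORR. It can count towards investigator-assessed confirmed ORR when the investigator calls PD and the central reader does not, and towards centrally assessed confirmed ORR only through an unscheduled confirming scan.

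The direction is certain: these rates can only rise, by 0.8 points per subject at N=123 and 1.7 at N=60. The total size is unknown, because the documents give no frequency for such subjects. It also depends on whether imaging continues after PD and whether radiotherapy closes the window. The conflict with PFS holds in any case; the −1.4 month duration holds only on the literal reading of Table 3. A claim that the trial's main ORR is materially inflated, or that its error rate is a particular figure, would go beyond the documents.

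**What to change.** - In SAP 7.5.1, 7.6.1, 7.6.2 and 7.6.3, and in Protocol 9.2.6.1.1, use assessments up to and including the first RECIST PD by the assessor being analysed, or up to subsequent anticancer therapy or retreatment, whichever is earliest.
- State whether radiotherapy given for progression counts as anticancer therapy for this purpose.
- Apply the same cut to the Stage 1 responder count.
- List responses recorded after progression separately, so the information is kept.
- Reconcile Protocol 6.4 with schedule note 21 on imaging after progression.

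Under this rule, a subject with PD at the Cycle 1 scan and no earlier response is a non-responder without clinical benefit and does not enter DOR or DOCB, so the negative duration in the example cannot arise. The cost is the wording and one programming condition. No new data are needed and the 60/63/123 design is unchanged. The rates may be slightly less favourable. The change concerns analysis rules only and takes no position on treatment beyond progression.
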